
Statistics
	
Three cohorts of patients will be prospectively included in the study:
 
1) Letrozole-stimulated cohort: this includes all newly diagnosed breast cancer who are candidates to receive (neo)adjuvant chemotherapy and undergo oocyte/embryo cryopreservation at the Belgian participating centres.
 
2) Standard-stimulated cohort: this includes all newly diagnosed breast cancer who are candidates to receive (neo)adjuvant chemotherapy and undergo oocyte/embryo cryopreservation at the French participating centres.
 
3) Non-stimulated cohort: this includes all newly diagnosed breast cancer who are candidates to receive (neo)adjuvant chemotherapy who have access

to the Fertility Clinics in all the participating centres but are not willing to undergo oocyte/embryo cryopreservation.

All the efficacy analyses will be performed to compare the letrozole-stimulated cohort and the standard-stimulated cohort. All the safety analyses will be conducted to compare separately the letrozole-stimulated cohort with the non-stimulated cohort and the standard-stimulated cohort with the non-stimulated cohort.

The sample size has been estimated based on the study primary endpoint (i.e. number of mature oocytes collected). With 113 patients in the standard-stimulated cohort and 113 in the letrozole-stimulated cohort, assuming a mean difference of 1.5 in the number of mature oocytes collected between the standard-stimulated cohort and the letrozole-stimulated cohort, the study will have a power of 0.80 to reject the null hypothesis of equal means with a standard deviation of 4.0 and with a significance level (alpha) of 0.05 using a two-sided two-sample equal-variance t-test. Considering that approximately one out of three (1:3) eligible patients counseled to undergo controlled ovarian stimulation for oocyte cryopreservation before starting anticancer treatments will accept the procedure, it is estimated to enroll 339 patients in the non-stimulated cohort.

Patients demographic, clinical and pathologic baseline characteristics will be compared in the three cohorts using chi-square test or Fisher Exact test for categorical variables and Wilcoxon rank-sum test or t-test for continuous variables, as appropriate. Dicothomous outcomes will be compared using

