### Secondary objectives:

- To evaluate the safety of performing controlled ovarian stimulation with or without letrozole in young women with newly diagnosed breast cancer and who are candidates to receive (neo)adjuvant chemotherapy in terms of complications associated with any of the procedure used for oocyte/embryo cryopreservation, invasive disease-free survival (iDFS), breast cancer-free interval (BCFI), overall survival (OS), kinetic of circulating tumor DNA (ctDNA) before and after stimulation.

The safety of performing controlled ovarian stimulation with or without letrozole will be evaluated in various subgroups of young women with newly diagnosed breast cancer who are candidates to receive (neo)adjuvant chemotherapy according to different patient, tumor or treatment characteristics.

- To evaluate baseline characteristics of young women with newly diagnosed breast cancer who undergo controlled ovarian stimulation with or without letrozole.

- To evaluate the characteristics of protocols with or without letrozole used for controlled ovarian stimulation in young women with newly diagnosed breast cancer who are candidates to receive (neo)adjuvant chemotherapy.

- To evaluate the efficacy of performing a controlled ovarian stimulation with or without letrozole in young women with newly diagnosed breast cancer who are candidates to receive (neo)adjuvant chemotherapy in terms of number of oocytes collected, maturation rate, number of oocyte/embryo cryopreserved, number of patients with poor response, and number of patients with stimulation failure. The efficacy of performing controlled ovarian stimulation with or without letrozole will be also evaluated in various subgroups of young women with newly diagnosed breast cancer who are candidates to receive (neo)adjuvant chemotherapy according to different patient, tumor or treatment characteristics.

- To evaluate the type and outcomes of assisted reproductive technology procedures in patients who return to the fertility clinic after the end of treatment. In patients with a clinically confirmed pregnancy obtained with assisted reproductive technology procedures after the end of treatment, pregnancy, fetal and obstetrical outcomes of the pregnancies will be evaluated.

- To evaluate the impact of anticancer therapies (chemotherapy with or without endocrine therapy with or without anti-HER2 agents) on patients' ovarian function.

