## 5. STATISTICS

Three cohorts of patients will be prospectively included in the study (Figure 1 in the Appendix):

**1) Letrozole-stimulated cohort:** this includes all newly diagnosed breast cancer who are candidates to receive (neo)adjuvant chemotherapy and undergo oocyte/embryo cryopreservation at the Belgian participating centres.

**2) Standard-stimulated cohort:** this includes all newly diagnosed breast cancer who are candidates to receive (neo)adjuvant chemotherapy and undergo oocyte/embryo cryopreservation at the French participating centres.

**3) Non-stimulated cohort:** this includes all newly diagnosed breast cancer who are candidates to receive (neo)adjuvant chemotherapy who have access to the Fertility Clinics in all the participating centres but are not willing to undergo oocyte/embryo cryopreservation. Patient who underwent another fertility preservation procedure (ovarian tissue cryopreservation, GnRH analogues,...) are eligible in this cohort.

All the efficacy analyses will be performed to compare the letrozole-stimulated cohort and the standard-stimulated cohort. All the safety analyses will be conducted to compare separately the letrozole-stimulated cohort with the non-stimulated cohort and the standard-stimulated cohort with the non-stimulated cohort.

To evaluate the efficacy of performing a controlled ovarian stimulation with or without letrozole in young women with newly diagnosed breast cancer who are candidates to receive (neo)adjuvant chemotherapy, the following endpoints will be assessed:

- Number of mature oocytes collected (primary endpoint).
- Number of oocytes collected;
- Maturation rate: defined as ratio between the number of mature oocyte collected and total number of oocyte collected;
- Number of oocyte/embryo cryopreserved;
- Number of patients with poor response: defined as retrieval of  $\leq 4$  oocytes;
- Number of patients with stimulation failure: defined as no follicular growth after 1 week of adequate controlled ovarian stimulation administration.

The efficacy of performing controlled ovarian stimulation with or without letrozole will be evaluated also in various subgroups of young women with newly diagnosed breast cancer who are candidates to receive (neo)adjuvant chemotherapy according to the following characteristics:

- Type of stimulation: follicular vs. random;
- Hormone receptor status: positive vs. negative;
- Presence of *BRCA* mutation: *BRCA*-mutated vs. *BRCA*-not mutated.

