To evaluate the safety of performing a controlled ovarian stimulation with or without letrozole in young women with newly diagnosed breast cancer who are candidates to receive (neo)adjuvant chemotherapy, the following endpoints will be assessed:

- Invasive disease-free survival (iDFS) defined as the time from study inclusion to the first appearance of the following invasive events: local recurrence, distant metastases, contralateral or ipsilateral breast tumor, second primary malignancy, or death from any cause;
- Breast cancer-free interval (BCFI) defined as the time from study inclusion to the first appearance of the following invasive events: local recurrence, distant metastases, contralateral or ipsilateral breast tumor;
- Overall survival (OS) defined as the time from study inclusion to death from any cause;
- Kinetic of circulating tumor DNA (ctDNA) assessed before, after stimulation and during study follow-up (if disease relapse).
- Complications associated with any of the procedure used for oocyte/embryo cryopreservation.

The safety of performing controlled ovarian stimulation with or without letrozole will be evaluated in various subgroups of young women with newly diagnosed breast cancer who are candidates to receive (neo)adjuvant chemotherapy according to the following characteristics:

- Stage at diagnosis: I vs. II vs. III;
- Hormone receptor status: positive vs. negative;
- HER2 status: positive vs. negative;
- Type of exposure to chemotherapy: prior to surgery (neoadjuvant) vs. post surgery (adjuvant);
- Exposure to endocrine therapy: exposure vs. no exposure;
- Presence of *BRCA* mutation: *BRCA*-mutated vs. *BRCA*-not mutated;
- Baseline ctDNA level: present vs. absent.

The following baseline characteristics of young women with newly diagnosed breast cancer who undergo controlled ovarian stimulation with or without letrozole will be assessed:

- Body-Mass Index (BMI) and body surface;
- Smoking history;
- Age at menarche;
- Prior pregnancies (completed, induced or spontaneous abortion);
- Prior treatment for infertility;
- Prior use of birth control pills;
- Prior gynecological diseases with potential impact on reproductive potential;
- Baseline ovarian reserve and function analysis.

Furthermore, the following characteristics of protocols with or without letrozole used for controlled ovarian stimulation in young women with newly diagnosed breast cancer who are candidates to receive (neo)adjuvant chemotherapy will be evaluated:

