The impact of anticancer therapies on patients' ovarian function will be evaluated in various subgroups of young breast cancer patients according to:

- Age: <30 vs. 30-35 vs. > 35;
- Type of chemotherapy received: anthracycline- and taxane-based vs. taxane-based vs. others;
- Number of months of chemotherapy received: <4 months vs. > 4 months;
- Exposure to platinum agents: use vs. no use.
- Exposure to endocrine therapy: use vs. no use.
- Exposure to anti-HER2 therapy: use vs. no use.
- Presence of *BRCA* mutation: *BRCA*-mutated vs. *BRCA*-not mutated.

The sample size has been estimated based on the study primary endpoint (i.e. number of mature oocytes collected). With 113 patients in the standard-stimulated cohort and 113 in the letrozole-stimulated cohort, assuming a mean number of mature oocytes collected of 6.1 in the standard-stimulated cohort, the study will have a power of 0.80 to reject the null hypothesis of equal means when the population mean difference is 1.5 mature oocytes collected (estimating a mean number of mature oocytes collected of 7.6 in the letrozole-stimulated cohort) with a standard deviation for both groups of 4.0 and with a significance level (alpha) of 0.05 using a two-sided two-sample equal-variance t-test. Considering that approximately one out of three (1:3) eligible patients counseled to

undergo controlled ovarian stimulation for oocyte cryopreservation before starting anticancer treatments will accept the procedure, it is estimated to enroll 339 patients in the non-stimulated cohort.

Patients demographic, clinical and pathologic baseline characteristics will be compared in the three cohorts using chi-square test or Fisher Exact test for categorical variables and Wilcoxon rank-sum test or t-test for continuous variables, as appropriate.

Dicothomous outcomes will be compared using univariate and multivariate logistic regression models. Time-to-event outcomes will be estimated and plotted using Kaplan-Meier methods. Survival rates will be compared using log-rank test and Cox proportional hazards models for univariate and multivariate analysis, respectively.

All tests will be two-sided and p-values of  $< 0.05$  will be considered statistically significant.

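### Procedure complications cannot be compared with the non-stimulated cohort, whose count is zero by definition; this one safety endpoint should be exempted from the general rule

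*Combined protocol and SAP*

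**What the plan says.** - **Comparison rule.** Section 5 says "All the safety analyses will be conducted to compare separately the letrozole-stimulated cohort with the non-stimulated cohort", and likewise for the standard-stimulated cohort. The Synopsis has the same rule: "All the safety analyses will be conducted to compare separately". Letrozole versus standard is assigned to the efficacy analyses. Neither place makes an exception.
- **Endpoint.** The safety endpoints in Section 5 are iDFS, BCFI, OS, ctDNA kinetics and "Complications associated with any of the procedure used for oocyte/embryo cryopreservation". The secondary objectives in Section 2 also name "complications associated with any of the procedure used for oocyte/embryo cryopreservation" under safety.
- **Control cohort.** Section 5 defines the non-stimulated cohort as women with access to the fertility clinics "but are not willing to undergo oocyte/embryo cryopreservation". It adds: "Patient who underwent another fertility preservation procedure (ovarian tissue cryopreservation, GnRH analogues,...) are eligible in this cohort".
- **Method.** "Dicothomous outcomes will be compared using univariate and multivariate logistic regression models" (Section 5). Fisher's exact test is named there only for baseline characteristics.
- **Data.** The collection list in Section 3.2 names no procedure-complication item. Section 7.2 exempts adverse events due to the malignancy or chemotherapy from CRF reporting, unless they are unexpected or suspected to be linked to the stimulation.

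**The concern.** The rule suits endpoints for which women in every cohort are at risk, such as recurrence and death. It does not suit an endpoint that exists only for women who have the procedure. Women outside the stimulated cohorts cannot have a complication of a retrieval they did not undergo, so the comparator is a fixed zero and not an estimate of a background rate. The comparison then tests only whether any complication occurred among treated women.

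The risk lies in reporting. A small p-value could be read as evidence of harm relative to a control, and a large one as reassurance. Neither reading would be justified. What is useful for counselling is how often complications occur under each protocol, and with what precision. The plan has no explicit rule for reporting that.

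**Working it through.** **Inputs.** 113 women per stimulated cohort and 339 in the non-stimulated cohort (Section 5). Let k be the number of women in one stimulated cohort with at least one procedure complication. Treating the endpoint as binary is an assumption. The documents give no expected complication rate, so k is varied.

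**The plan's own figure.** The 113 per cohort comes from the primary endpoint (difference 1.5, SD 4.0, two-sided alpha 0.05, two-sample t-test). The exact noncentral-t power at 113 per group is 0.801, which matches the stated 0.80. No figure is stated for any safety endpoint.

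**Step 1: the control count.** The endpoint concerns oocyte/embryo cryopreservation procedures, and the control cohort does not undergo them. Its count is therefore 0/339 whatever the safety of stimulation. Ovarian tissue cryopreservation and GnRH analogues are allowed in that cohort, but their complications lie outside the endpoint as worded.

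**Step 2: the planned model.** The odds ratio is [k/(113 − k)] / [0/339], which is infinite for any k ≥ 1. The log odds ratio has no finite maximum-likelihood estimate.

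**Step 3: what a p-value would measure.** The likelihood-ratio statistic for k/113 versus 0/339 (total 452) is

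G = 2{[k ln(k/113) + (113 − k) ln(1 − k/113)] − [k ln(k/452) + (452 − k) ln(1 − k/452)]}, on 1 df.

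For k = 1: G = 2[−5.723 − (−7.113)] = 2.78, p = 0.096.

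The two-sided Fisher p for these tables equals C(113, k)/C(452, k). For k = 1 this is 113/452 = 0.25. For k = 2 it is (113 × 112)/(452 × 451) = 0.062.

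| k of 113 | G | Likelihood-ratio p | Fisher p |
|---|---|---|---|
| 1 | 2.78 | 0.096 | 0.25 |
| 2 | 5.57 | 0.018 | 0.062 |
| 3 | 8.38 | 0.0038 | 0.015 |
| 4 | 11.20 | 0.0008 | 0.0038 |

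Both columns depend on k alone, because the control cell cannot vary. Three complications in 113 women (2.7%) are enough for p < 0.05 on either test.

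**Step 4: what can be estimated instead.** The exact (Clopper-Pearson) 95% CI within one stimulated cohort is 0.0–4.8% for 1/113, 0.6–7.6% for 3/113 and 2.0–11.2% for 6/113. For letrozole minus standard with equal counts of 1, 3 or 6 per cohort, the difference is 0, with Newcombe 95% limits of ±4.0, ±5.2 or ±6.5 percentage points.

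**The case against.** The strongest reply is that the rule governs comparisons only. Section 5 says complications will be assessed for stimulation with or without letrozole, and nothing bars a table of counts by cohort. An analyst who sees a zero cell would probably describe the data and move on. This stands in part: the data are not lost and per-cohort description is open. It does not rescue the written comparison, which covers all safety analyses and cannot be carried out meaningfully here. It is also fair that the plan never makes the endpoint dichotomous. The failure of the logistic model depends on that assumption; the zero in the control cohort does not.

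A reader might infer three stronger points, and the documents do not support them.

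- **That the lack of a letrozole versus standard safety test is itself an error.** Protocol and country coincide: the standard cohort is made up of women who "undergo oocyte/embryo cryopreservation at the French participating centres", and the letrozole cohort comes from Belgian centres. Choosing the non-stimulated cohort as the safety comparator is defensible for the other endpoints. The Background calls for exploring differences between protocols but does not promise a head-to-head safety test.
- **That the ctDNA comparison fails in the same way.** Table 1 marks the plasma draw at the end of stimulation as mandatory and does not separate the cohorts. It is not established that non-stimulated women lack that sample.
- **That the model would yield a particular misleading Wald p-value.** With no finite estimate, what is printed depends on the fitting routine and where it stops, so no such figure is used here.

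**Conclusion.** The point holds for one of the five safety endpoints. For procedure complications, the prescribed comparison with the non-stimulated cohort is void because the control count is zero by definition. This follows from the wording of the endpoint and of the cohort, and needs no assumed rate. The p-values in the table rest on two further assumptions: that the variable is women with at least one complication, and that the cohorts reach their planned sizes.

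The consequence is limited. iDFS, BCFI, OS, the primary endpoint and the sample size are unaffected, and complications can still be described in each cohort. Severity is minor: a rule that fails as written for a secondary endpoint and is easily put right.

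**What to change.** 1. In Section 5 and the Synopsis, exempt procedure complications from the comparison with the non-stimulated cohort. Leave the rule in place for the other safety endpoints.
2. Define the variable as women with at least one complication of a procedure used for oocyte or embryo cryopreservation.
3. Report the number, rate and exact 95% CI in each stimulated cohort. Add the letrozole minus standard risk difference with its 95% CI, as description without a test, and state that it is confounded with country (Belgian versus French centres).
4. Add a procedure-complication item to the data list in Section 3.2. The reporting provision in Section 7.2 does not replace it, since it keeps only events that are unexpected or suspected to be linked to the stimulation and names no item for complications of retrieval.

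**Cost.** A few sentences and one eCRF item, with no extra patients. A nominal comparison is given up. The contrast that replaces it is imprecise (about ±4.0 to ±6.5 points at 1 to 6 events per cohort) and cannot separate protocol from country.

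### The survival safety comparisons set each single-country stimulated cohort against a two-country control cohort; a country-stratified sensitivity analysis would guard cheaply against a possible country difference

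*Combined protocol and SAP*

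**What the plan says.** Section 5 (Statistics) and the Synopsis define the three cohorts partly by country. The letrozole-stimulated cohort is made up of women who "undergo oocyte/embryo cryopreservation at the Belgian participating centres", and the standard-stimulated cohort of women who "undergo oocyte/embryo cryopreservation at the French participating centres". Section 1 gives the reason: letrozole may not be used for stimulation in France. The non-stimulated cohort is women "who have access to the Fertility Clinics in all the participating centres but are not willing to undergo oocyte/embryo cryopreservation", so it mixes both countries. The planned sizes are 113, 113 and 339.

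Under Section 5, the safety analyses will "compare separately the letrozole-stimulated cohort with the non-stimulated cohort and the standard-stimulated cohort with the non-stimulated cohort". The Synopsis states the same plan: "All the safety analyses will be conducted to compare separately the letrozole-stimulated cohort with the non-stimulated cohort", and likewise for the standard-stimulated cohort. The safety endpoints in Section 5 include iDFS, BCFI and OS. For these, "Survival rates will be compared using log-rank test and Cox proportional hazards models for univariate and multivariate analysis, respectively". No stratification factor or Cox covariate is named.

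Two other planned analyses bear on the point. "The safety of performing controlled ovarian stimulation with or without letrozole will be evaluated in various subgroups", and the seven subgroup factors listed do not include country. "Patients demographic, clinical and pathologic baseline characteristics will be compared in the three cohorts", that is, between cohorts and not between Belgian and French non-stimulated women.

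**The concern.** In the stimulated cohorts, protocol and country coincide; in the control cohort, countries are mixed. A pooled comparison therefore sets Belgian women against a Belgian-French mixture, and then French women against the same mixture. Any country difference in the underlying hazard enters both contrasts, with opposite signs, for all three endpoints. A difference in how readily recurrence is detected would act in the same way, mainly on iDFS and BCFI and much less on OS.

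At stake is the reading of the safety results. One protocol could look safer, and the other less safe, than no stimulation when neither has an effect. In the letrozole-versus-standard efficacy comparison, country cannot be separated from protocol. Here it can, because non-stimulated women are enrolled in both countries.

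**Working it through.** **The plan's own figure.** For the primary endpoint (difference 1.5, SD 4.0, two-sided alpha 0.05), exact t-test power is 0.798 with 112 per cohort and 0.801 with 113, so the stated 113 reproduces. No event number, hazard ratio or power is stated for iDFS, BCFI or OS, so what follows rests on assumptions.

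**Inputs.** From Section 5: 113 stimulated women per country and 339 controls. Assumed: p, the Belgian share of controls; r, the French/Belgian hazard ratio; 15% events in Belgian women; no true effect of stimulation. Section 5 gives a single uptake figure of about one in three. With equal stimulated numbers, an even split (p = 0.5, about 170 controls per country) follows only if uptake is the same in both countries.

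**Bias of the unadjusted hazard ratio.** The pooled control hazard, relative to Belgium, is h = p + (1 - p)r. The expected hazard ratios are 1/h for letrozole and r/h for standard stimulation.

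- p = 0.5, r = 0.8: h = 0.90; 1.11 and 0.89
- p = 0.5, r = 1.0: h = 1.00; 1.00 and 1.00
- p = 0.5, r = 1.3: h = 1.15; 0.87 and 1.13
- p = 0.5, r = 1.5: h = 1.25; 0.80 and 1.20
- p = 0.25, r = 1.3: h = 1.225; 0.82 and 1.06
- p = 0.75, r = 1.3: h = 1.075; 0.93 and 1.21

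**False-positive risk of the pooled test.** French events are 1 - 0.85^r. The standard error (SE) of the log hazard ratio is sqrt(1/events stimulated + 1/events controls). The risk is Phi(-1.96 + |log HR|/SE) + Phi(-1.96 - |log HR|/SE).

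For r = 1.3, p = 0.5:

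- French event share: 1 - 0.85^1.3 = 0.190.
- Events: letrozole 113 x 0.15 = 17.0; standard 113 x 0.190 = 21.5; controls 169.5 x 0.15 + 169.5 x 0.190 = 57.7.
- Letrozole: SE = 0.276, |log HR| = 0.140, risk 0.080.
- Standard: SE = 0.253, |log HR| = 0.123, risk 0.077.

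The same steps give 0.066 and 0.067 at r = 0.8, and 0.129 and 0.119 at r = 1.5. Over 10-20% events and these ratios the range is about 6-16%.

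**Check by simulation** (2,000 runs per setting, even split, 15% Belgian events at five years, no true effect). Log-rank rejection rates, letrozole/standard:

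- r = 1.0: pooled 0.051/0.051, stratified by country 0.051/0.052
- r = 1.3: pooled 0.072/0.082, stratified 0.048/0.049
- r = 1.5: pooled 0.097/0.134, stratified 0.049/0.045

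**Price of stratifying.** A stratum without stimulated women carries no information on the contrast, so only same-country controls count. With equal event shares and a same-country control share s, the SE ratio is sqrt[(1/113 + 1/(339s)) / (1/113 + 1/339)]. This is 1.04 at s = 0.75, 1.12 at s = 0.50 and 1.32 at s = 0.25.

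For power, take a true hazard ratio of 2.0, 15% control events, common follow-up and r = 1. The stimulated event share is then 1 - 0.85^2 = 0.2775, or 31.4 events. Pooled controls give 50.9 events (SE 0.227, power 0.86). Half of them give 25.4 events (SE 0.267, power 0.74). Simulation gave 0.83-0.85 pooled and 0.75-0.76 stratified, so about 0.84 against 0.75.

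**The case against.** The strongest reply is that the harm is hypothetical. Eligibility and endpoint definitions are common to both countries, and nothing in the documents shows a Belgian-French difference in hazard or detection. At ratios of 0.8 or 1.3 the false-positive risk rises only to about 7-8%. This stands, and it limits the point to a vulnerability.

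The plan also has a multivariate Cox model, which could include country. That stands too. It does not protect the log-rank and unadjusted results, and adjusting for stage, receptors and treatment would remove only what those factors explain.

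A reader might infer that no planned analysis could reveal a country effect. That goes too far. Because cohort and country coincide among stimulated women, the three-cohort baseline comparison could show case-mix differences between Belgian and French women. It would not isolate an unmeasured difference in hazard or detection.

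A reader might also infer that the stratified analysis should replace the pooled one. The figures do not support that. At an even split and 15% events, root-mean-square error of the log hazard ratio (letrozole/standard) is 0.30/0.33 pooled against 0.31/0.35 stratified at r = 0.8, 0.28 against 0.31 at r = 1.0, and equal to two decimals at r = 1.3. Stratifying is better for both cohorts only at r = 1.5.

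Finally, two analyses of equal rank would muddle the reading. In simulation with no country difference and a true hazard ratio of 2.0, the two log-rank tests disagreed on significance in about 13% of studies. This stands, so one analysis must be named in advance as the main one.

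**Conclusion.** The point holds as a minor, cheap improvement on secondary endpoints for which the study was not sized. The pooled, unadjusted survival comparisons are open to country confounding that pushes the two protocols in opposite directions. The size depends wholly on an unknown country ratio and control split: nothing at 1.0, modest at 1.3 and material at 1.5.

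The documents do not support saying that the safety results will be biased, or in which direction. Nor does the point touch the primary analysis. Stratifying by country also leaves untouched the self-selection of women who decline the procedure.

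**What to change.** In Section 5 and the Synopsis:

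- Keep the planned pooled comparison and state that it remains the main result.
- Add one prespecified sensitivity analysis for iDFS, BCFI and OS: a log-rank test and a Cox model stratified by enrolling country. Letrozole-stimulated women are then compared with Belgian, and standard-stimulated women with French, non-stimulated women.
- Include country in the multivariate Cox model.
- State that robustness will be judged by comparing hazard ratios and confidence intervals, not by whether both analyses reach p < 0.05. A shift in the estimate points to country confounding. A wider interval around a similar estimate does not weaken a signal of harm.

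The cost is a few sentences. Enrolling country follows from the centre, so no new data are needed. The sensitivity analysis is less precise, as shown above, and there is a second set of survival results to report; the main analysis keeps its precision.
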